## **Study Outcomes**

1. In the treatment group, we expect a 20% total reduction in face to face encounters (defined as unscheduled sick visits, emergency room visits, and hospital admissions) for respiratory symptoms with the prophylactic use of azithromycin, as compared to the control group.
  - a. In the treatment group, we expect to have a 20% decrease in the number of unscheduled sick visits due to respiratory illness during the 3-6 month study period with the prophylactic use of azithromycin, as compared to the control group .
  - b. In the treatment group, we expect to have a 20% decrease in the number of Emergency Room visits due to respiratory illness during the 3-6 month study period with the prophylactic use of azithromycin, as compared to the control group.

- c. In the treatment group, we expect to have a 20% reduction in the number of hospital admissions due to respiratory illness during the 3-6 month study period with the prophylactic use of azithromycin, as compared to the control group.
2. In the treatment group, we expect a 10% total reduction (as compared to baseline) in the level of myeloperoxidase in the nasopharyngeal secretions collected during respiratory illnesses that require a face to face provider encounter, as compared to the control group.
3. In the treatment group, we expect a 10% total reduction in the level of pro-inflammatory cytokines in the nasopharyngeal secretions collected during respiratory illnesses that require a face to face provider encounter, as compared to the control group.
4. In the treatment group, we expect a 10% reduction from baseline in the level of airway obstruction as measured by a tremoFlo Airwave Oscillometry System during the 3-6 month study period, respiratory illness and at the conclusion of the intervention phase.
5. We expect no significant difference in adverse side effects between the treatment group receiving the macrolide and the control group receiving the placebo during the 4 month study.
6. We expect the intervention to be cost-effective from a healthcare system perspective.

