### **Exploratory Outcomes:**

1. Using a standardize nasal wash procedure, respiratory samples will be collected at enrollment, at end of study, and during acute respiratory illness requiring face-to-face provider interaction. Children with a tracheostomy will have both a nasal wash sample and a tracheal aspirate sample collected. The respiratory samples will be stabilized with a universal transport media, processed and stored at -80 C for future testing. Testing will be performed for cytokines/chemokines; other biomarkers of disease such as LDH, MPO, and caspase; viral and bacterial respiratory pathogens; and microbiome.
2. To determine if prophylactic use of azithromycin will reduce level of airway resistance as measured by an Airwave Oscillometry System in subjects above 2 years of age, at the time of respiratory illnesses, during the 3-6 months intervention.
3. To determine if prophylactic use of azithromycin will reduce the total number of unscheduled face-to-face physician visit for respiratory related illness in a clinic, urgent care, emergency room or hospital setting during the following 12 months after the intervention.

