reactions. In addition, there may be an increased risk of diaper rash and/or oral thrush with the increased use of antibiotics. Another adverse outcome of azithromycin has been an increase in pyloric stenosis with both prenatal and infant exposure for the first 4 months of life, and benefit in this age group must outweigh this potential risk. However, our population for this project will begin at 6 months of age. Each of these risks and any other unexpected outcomes will be monitored at any visits to the clinic, or with biweekly phone calls if no visits have been scheduled in the previous two weeks. The primary benefit we hope to see is a reduction in the number of respiratory illness related office visits. With the anti-inflammatory properties of the macrolide, we predict an overall reduction in the severity of respiratory illnesses during the study period. Additionally, we will monitor data for a 2 month period following last azithromycin administration. This reduction may lead to a decrease in the number of unscheduled office visits, emergency room visits, and hospital admissions. With less face to face provider encounters, there will be less opportunity for potential exposure to other viruses, as well as less time away from home or work for the patients' parents and, potentially, decreased health care related costs.

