### **Interpretation and Potential Importance of Findings**

A substantial portion of our high risk chronically ill children have some form of chronic lung disease, including patients with tracheostomies, bronchopulmonary dysplasia, and chronic respiratory failure requiring mechanical ventilation. Most of the hospital admissions in this group of patients were related to respiratory infections in children less than 6 years of age (37% during the winter season for the previous 3 years). Despite vaccination rates of nearly 100% and 24/7 access to our clinic, viral respiratory illnesses continue to cause considerable morbidity and high healthcare costs. Innovative new prophylactic treatments are needed.

With this proposal, we will determine if the prophylactic use of azithromycin will 1) reduce the number of days when unscheduled medical treatment health care related encounters was given outside the home, 2) reduce the number of emergency room visits, hospitalizations and clinic visits due to respiratory illness, 3) reduce the level of myeloperoxidase and pro-inflammatory cytokines during viral illnesses requiring face to face physician interaction, 4) demonstrate a reduction in airway obstruction as measured by an oscillometer 5) have a similar safe profile compared to the placebo, and 6) demonstrate cost-effectiveness of macrolides use. Understanding the anti-inflammatory effects of azithromycin when used as a prophylactic drug will provide important insight into the prevention of more serious sequelae of respiratory infections. In particular, this proposal will contribute to understanding disease in children ages 6 months to 6 years with chronic lung disease, a population that has a higher rate of hospitalizations for respiratory symptoms.

3. Society AT. *Statement on the Care of the Child with Chronic Lung Disease of Infancy and Childhood* 2002. Accessed 8/19/14.

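### The stated between-arm marker comparison uses only illnesses that led to an encounter, and no end-of-treatment marker analysis is specified

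*Combined protocol and SAP*

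**What the plan says.** Study Outcomes, item 2, expects a 10% reduction, relative to baseline and to control, "in the level of myeloperoxidase in the nasopharyngeal secretions collected during respiratory illnesses that require a face to face provider encounter". Item 3 puts the same restriction on pro-inflammatory cytokines. The closing section, Interpretation and Potential Importance of Findings, repeats it: the trial will determine whether azithromycin will "reduce the level of myeloperoxidase and pro-inflammatory cytokines during viral illnesses requiring face to face physician interaction".

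The same plan expects treatment to change the event that triggers sampling. In item 1, "we expect a 20% total reduction in face to face encounters". Under Risks, "we predict an overall reduction in the severity of respiratory illnesses during the study period".

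Samples are also planned outside illness. Exploratory Outcomes, item 1, states that "respiratory samples will be collected at enrollment, at end of study, and during acute respiratory illness requiring face-to-face provider interaction". The design Overview and Laboratory Evaluation agree that each child has a first and a final nasal sample.

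The Data Analysis Plan promises frequentist and Bayesian intent-to-treat analyses in general terms, and Sample size and power promises Bayesian estimates for secondary outcomes. The only outcomes that the Data Analysis Plan names are hospital days, ER visits and unscheduled clinic visits.

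For oscillometry, item 4 reads "we expect a 10% reduction from baseline in the level of airway obstruction as measured by a tremoFlo Airwave Oscillometry System". Unlike items 1 to 3, it names no control group.

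**The concern.** Whether an illness leads to an encounter is decided after randomisation, and the plan expects azithromycin to influence it. Comparing markers only among those illnesses sets two selected groups side by side. If azithromycin prevents some visits, the illnesses still seen on azithromycin need not be the same kind as those seen on placebo. A marker difference could then reflect which illnesses were sampled, and a lack of difference could hide a real effect. The reference to baseline in item 2 does not repair this: a child's value at enrolment says nothing about which of that child's later illnesses reached a provider.

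This matters because the title of the trial is its anti-inflammatory effect, and the hypothesis at the end of the Background links less severe illness to a restrained inflammatory cascade. The comparison that randomisation would support, at the end of treatment in all children with a final sample, has its material collected but no stated analysis.

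**Working it through.** **Step 1: is the comparison conditional on treatment?** Items 2 and 3 and the closing section restrict the samples to encounter illnesses. Item 1 and Risks expect azithromycin to reduce encounters and severity. On the plan's own expectations, treatment affects entry into the comparison.

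**Step 2: the plan's own figure.** No sample size or power is stated for any marker. The stated calculation is for encounters: 45 per group, SD 1.66, difference 1, two-sided alpha 0.05. A two-sample t-test gives 80.7% power, so the stated 80% reproduces. Its rate and SD are used below.

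**Step 3: how many children could give an illness sample?** This concerns precision, not bias. Inputs: 1.6 encounters per child-year and SD 1.66 (Sample size and power); 20% fewer on azithromycin (item 1); 92 children, taken as 46 per arm (Overview); 3 to 6 months of treatment. Assumed: negative binomial counts and an even rate over the year.

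- Dispersion = (1.66² − 1.6) / 1.6² = (2.7556 − 1.6) / 2.56 = 0.451; shape = 1 / 0.451 = 2.215.
- P(at least one) = 1 − (1 + 0.451 × mean)^(−2.215).

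| Months | Placebo mean | Placebo P | Azithromycin mean | Azithromycin P | Children of 92 |
|---|---|---|---|---|---|
| 3 | 0.40 | 0.308 | 0.32 | 0.258 | 14.2 + 11.9 = 26.0 |
| 6 | 0.80 | 0.495 | 0.64 | 0.430 | 22.8 + 19.8 = 42.5 |

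So about 26 to 43 children would have an encounter, and could give an illness sample if every encounter were sampled. Treatment runs in the respiratory season, so an even rate may be too low; at an assumed 1.5 times the annual rate the range is 35.2 to 53.6. Limitations says samples from the ED, weekends and after hours are hard to obtain. With 75% of encounters sampled (assumed, even annual rate) the range is 20.7 to 35.2, and with 50% it is 14.6 to 26.0. Up to 92 children could have a final sample.

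**Step 4: can the bias be sized?** Not from the documents. One illustration assumes that half of control illnesses reach an encounter, that azithromycin has no direct marker effect, that the marker correlates 0.3 to 0.7 with severity, and that log-SD is 0.5 to 1.0. With 20% fewer encounters, the azithromycin/placebo ratio becomes 1.026 to 1.125. Applied to a true 0.90, it gives 0.90 × 1.026 = 0.92 to 0.90 × 1.125 = 1.01. Every input is assumed. If the visits prevented were instead those with the highest marker levels, the shift would run the other way.

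**Step 5: what would an end-of-treatment analysis deliver?** Assumed: log-SD 0.5 to 1.0, baseline-final correlation 0.5, true ratio 0.90. SE of the log ratio = SD × √(1 − 0.5²) × √(2/n), with 2n − 3 degrees of freedom.

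| n per arm | log-SD | SE | Power | 95% interval around 0.90 |
|---|---|---|---|---|
| 46 | 0.5 | 0.090 | 0.21 | 0.75 to 1.08 |
| 46 | 1.0 | 0.181 | 0.09 | 0.63 to 1.29 |
| 37 (20% missing) | 0.5 | 0.101 | 0.18 | 0.74 to 1.10 |
| 37 (20% missing) | 1.0 | 0.201 | 0.08 | 0.60 to 1.34 |

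**The case against.** The strongest reply is that illness samples are the right ones. The hypothesis in the Background is about severity and inflammation during viral illness, and items 2 and 3 measure exactly that. This stands: the comparison should be kept, and an end-of-treatment analysis does not replace it. What it lacks is a statement that it is conditional on an encounter.

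Second, the markers are listed as exploratory in a self-described pilot. Laboratory Evaluation speaks of secondary hypotheses, but under either label they are not primary. This also stands, and limits the weight of the point.

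Third, the general intent-to-treat and Bayesian statements could be taken to cover the markers. They show an intention to analyse by arm, but they name no marker or time point, while items 2 and 3 do name one: illness.

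Fourth, item 4 can be read as implying a placebo comparison, since this is a placebo-controlled trial and the matching exploratory aim asks whether azithromycin reduces airway resistance. That is a fair reading, so the missing control in item 4 is a wording point only. So is the difference in timing: the exploratory aim places oscillometry "at the time of respiratory illnesses, during the 3-6 months intervention", while item 4 adds the end of the intervention.

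A reader might go further and infer that a true benefit would be masked, because the mildest visits are the ones lost. The documents do not support that. They do not say which visits would be prevented, and milder illness overall could leave the observed azithromycin episodes no sicker than the placebo ones.

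**Conclusion.** The point holds in a limited form. The only between-arm marker comparison that the plan states is restricted to a post-randomisation event that treatment is expected to change, and no section specifies a between-arm analysis of the end-of-treatment samples. A true marker effect could be attenuated, masked or exaggerated; the documents fix neither direction nor size. The counts of 26 to 43 children (even rate) or 35 to 54 (assumed winter rate) describe how much illness material might exist. They are not a measure of bias or an upper limit, and they rest on the negative binomial assumption and the 20% reduction.

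It should not be inferred that the trial's main result is compromised: the encounter outcome does not depend on this comparison. This is an inexpensive improvement to consider, not a defect that must be corrected before the trial can be interpreted.

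**What to change.** 1. Add to the Data Analysis Plan one exploratory between-arm ANCOVA of end-of-treatment log myeloperoxidase and log cytokines, adjusted for the baseline value, in children with a final sample and analysed as randomised. Report the azithromycin/placebo ratio with its 95% interval, the number of missing final samples per arm, and the number of final samples taken during an acute respiratory illness.
2. Keep the illness-sample comparison for the during-illness hypothesis. In Study Outcomes and in the closing Interpretation section, label it as conditional on an encounter and not protected by randomisation, and report children and samples per arm.
3. Minor: word item 4 as azithromycin versus placebo for the end-of-intervention reading, adjusted for the baseline reading, in children with both. The closing section's promise to "demonstrate a reduction in airway obstruction as measured by an oscillometer" can follow the same wording.

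The cost is wording; no sample or visit is added. Laboratory Evaluation keeps specimens frozen until the trial is complete, so the analysis can be fixed before any assay.

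The downsides are real. End-of-treatment samples largely reflect inflammation outside illness, which is a different question from the one in the Background. Some final samples may be missing, because Study Procedures plans no additional visits, and children with a final sample are then themselves a post-randomisation subset. With power of about 8% to 21% for a 10% reduction, the result is an estimate with an interval, not a powered test.

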### **Secondary Aim:**

1. To determine if the administration of azithromycin will have similar number of adverse side effects, or adverse events leading to unscheduled clinic, urgent care, emergency room or hospital visit as compared to placebo during the 3-6 month study period and the following 2 months.
2. To determine if the use of azithromycin will reduce healthcare cost associated with respiratory illness during the 3-6 month study period and 2 month follow-up period.

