#### *Study Procedures:*

Patients will be randomized by the REDCap statistical program in a double blind manner. Parents will then be provided with a medication or placebo for the duration of the study. Patients would be recruited for this study on a rolling basis from October 1st to December 31st, and all patients completing the intervention part of the protocol on 31st March at the end of the season. Half of the patients will receive azithromycin at a

dose of 5 mg/kg to be given once a day on Monday, Wednesday, and Friday. The other half, the control group, will be provided with a placebo medication of similar taste, color, texture, and consistency, also to be taken once a day on Monday, Wednesday, and Friday. Both the study medication and the placebo will be dispensed from Corner Compounding Pharmacy, mixed with a fish-oil base to ensure a shelf life of more than six months, and flavored with citrus to improve palatability. Parents will be contacted biweekly, either in clinic or by phone, to monitor for any adverse reactions, including rash, nausea, vomiting, diarrhea, or abdominal cramping. If a significant adverse reaction occurs, the medication will be discontinued. If an allergic reaction (such as rash or shortness of breath) is noted, the blind will be broken by Research Coordinator [name], who is not involved with the project. This un-blinding will be done to note if it is an allergy to the medication.

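### The safety aim asks whether azithromycin is similar to placebo, but its only criterion is non-significance, which 46 children per arm cannot turn into evidence of similarity, over a 4-month window that conflicts with the rest of the protocol

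*Combined protocol and SAP*

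**What the plan says.** Secondary Aim 1 is to determine whether azithromycin "will have similar number of adverse side effects, or adverse events leading to unscheduled clinic, urgent care, emergency room or hospital visit", and it sets the period: "as compared to placebo during the 3-6 month study period and the following 2 months". The Interpretation and Potential Importance of Findings section repeats the promise. It lists, among the things the trial will determine, whether the drug will "have a similar safe profile compared to the placebo".

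Item 5 of Study Outcomes is the only place that says what result would bear on this aim: "We expect no significant difference in adverse side effects" between the two arms. It places the comparison "during the 4 month study".

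No margin, interval rule, assumed placebo adverse-event rate or safety power appears anywhere. The Data Analysis Plan models hospital days, ER visits and unscheduled clinic visits for respiratory symptoms, and does not mention adverse events. The Sample size and power section accepts that power is lower for secondary outcomes and offers a Bayesian probability of benefit for them.

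**The concern.** An aim to show similarity needs a statement of how large a difference the data exclude. A non-significant test does not give that. In a small trial it can arise because the arms are alike or because there is too little information to separate them. If item 5 is used to answer the aim, a report could describe azithromycin as similar to placebo when a substantial excess of adverse events is still compatible with the data. The children are medically complex and take the drug for months, so readers would rely on that statement.

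The window is a second problem. The 4-month period in item 5 matches no period defined elsewhere. An analyst who followed it would leave out on-drug and post-drug events that Secondary Aim 1 says should count.

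**Working it through.** **Inputs from the documents.** Overview: 92 children. Study Procedures: half to each arm, so 46 per arm. Sample size and power: two-sided alpha 0.05. The Overview also calls 92 a minimum for Season 1, so the number could be higher, but no larger target is given. No dropout rate is stated, and children who stop medication are still followed, so I apply no loss.

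**Assumption.** The placebo proportion with at least one adverse event is not given. I show 10%, 20% and 30%, and comment on other values.

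**Step 1. The plan's own sample size (primary outcome).** With a difference of 1 and SD 1.66, n = 2 × (1.96 + 0.842)² × 1.66² / 1² = 43.3, so 44 per arm. The t-test version gives 44.2, so 45, as the plan states. This calculation does not cover safety.

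**Step 2. Power to detect a true doubling, 46 per arm.** The normal approximation is power = Φ{[d − 1.96·√(2p̄(1−p̄)/n)] / √[(p₁(1−p₁) + p₂(1−p₂))/n]}, where d = p₂ − p₁ and p̄ is the mean of p₁ and p₂. For 10% vs 20%: (0.10 − 1.96 × 0.0745)/0.0737 = −0.62, so power is 0.267. Enumerating all outcomes exactly gives:

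| Placebo vs azithromycin | Fisher power | Chi-square power | Doubling missed |
|---|---|---|---|
| 10% vs 20% | 18% | 28% | 72-82% |
| 20% vs 40% | 47% | 56% | 44-53% |
| 30% vs 60% | 77% | 83% | 17-23% |

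Below this range power falls further (5% vs 10%: 6-17%). Above it, a doubling is nearly always found (40% vs 80%: 97-98%). For 80% power to detect a doubling, the approximation needs 199, 82 or 42 per arm at placebo rates of 10%, 20% or 30%.

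**Step 3. What balanced data would exclude.** Suppose the observed rates were identical.
- Half-width of the 95% interval for the risk difference, 1.96·√(2p(1−p)/46): 12 points at 10%, 16 at 20%, 19 at 30%.
- Upper 95% limit for the risk ratio, exp{1.96·√(2(1−p)/(46p))}: 3.4, 2.3 and 1.9.

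At 10% or 20%, even perfectly balanced results would not rule out a doubling. At 30% they just would.

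**Step 4. Event counts.** Secondary Aim 1 speaks of a number of events. Using a Wald test on the log rate ratio, Poisson power for a doubled rate is 23%, 40%, 56%, 78% and 97% at 0.1, 0.2, 0.3, 0.5 and 1.0 placebo events per child. With overdispersion (dispersion 1) it falls to 56% at 0.5 and 71% at 1.0.

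**Step 5. The window.** Study Procedures states: "Patients would be recruited for this study on a rolling basis from October 1", closing on 31 December, with all children finishing treatment on 31 March. The Overview continues data collection to 31 May. Dropping everything after month 4 removes:

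| Enrolled | On drug | Total | On-drug time dropped | Total time dropped |
|---|---|---|---|---|
| 1 October | 6 months | 8 months | 2 of 6 (33%) | 4 of 8 (50%) |
| 1 December | 4 months | 6 months | none | 2 of 6 (33%) |
| 31 December | 3 months | 5 months | none | 1 of 5 (20%) |

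The loss is greatest for the children exposed longest.

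**The case against.** The strongest reply is that item 5 is a prediction. All six items in Study Outcomes state what the investigators expect, and neither the Data Analysis Plan nor the power section says that non-significance will be read as similarity. That stands: a reader might infer a formal decision rule, and the documents do not contain one. But without item 5 the aim has no criterion at all, so the gap remains.

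The second reply is that the size of the problem depends on a rate the documents do not give. This also stands. A reader might infer that the trial would find similar safety whatever the truth, and the documents do not support that. Parents are asked every two weeks about rash, nausea, vomiting, diarrhea and cramping. A placebo rate of 30% or more is therefore possible, and there a doubling would usually be detected.

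The third reply concerns the window. A reader might infer that later safety data would not exist. They would: Secondary Aim 1, the Overview and the Risks section all provide for 2 months of monitoring after treatment. The 4-month phrase stands alone against them and may be leftover text. The harm arises only if the analysis follows it, but the conflict still has to be resolved.

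The fourth reply is that this is a pilot, that the plan already promises 95% credible intervals, and that a formal margin is out of proportion. On the margin the reply is right. To rule out a 10-point excess with 80% power (one-sided 0.025, equal true rates), n = (1.96 + 0.842)² × 2p(1−p)/margin² gives 142, 252 or 330 per arm at 10%, 20% or 30%. For 15 points it gives 63, 112 or 147; for 20 points, 36, 63 or 83. Of these, only a 20-point margin at a 10% rate fits 46 per arm. The promised intervals are not tied to adverse events, and a probability of benefit is not a criterion for similar harm.

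**Conclusion.** The concern holds in a limited form. The protocol promises a conclusion about similarity and offers only an expected non-significant result in support. At 46 per arm that result is weak evidence when placebo adverse-event rates are low to moderate, and Step 3 shows that balanced data would still leave a doubling open at 10% or 20%. The argument loses most of its force at about 30% and above, or at about one event per child without overdispersion. These figures assume 92 children, equal allocation, no loss to follow-up and the stated range of placebo rates.

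The 4-month window is a plain inconsistency whatever the rate. Its effect on the analysis depends on whether anyone applies it literally. The primary outcome is not affected by either point.

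**What to change.** 1. Delete the 4-month phrase from item 5 and use the window in Secondary Aim 1 (treatment plus 2 months).
2. Add a short adverse-event analysis to the Data Analysis Plan. Report events by arm, as randomized, as a risk difference and a rate ratio with 95% intervals. Allow for follow-up of 5 to 8 months, for example with a log follow-up-time offset in the rate model. A posterior probability of excess harm could be added.
3. State that a non-significant difference will not be reported as similarity, and that the report will give the largest excess not ruled out.
4. A margin is optional. If the investigators want one, it should be fixed before unblinding, with an acknowledgement that this sample can support only a wide one.

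The cost is more than a wording change, because the planned regression names only respiratory encounters and an adverse-event analysis has to be added. That analysis is small and needs no extra children, visits or data. The other cost is a more modest safety conclusion.
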